7.3.3 Immediate Reporting of Adverse Events to the Sponsor and to Merck

7.3.3.1 Serious Adverse Events

A serious adverse event is any adverse event occurring at any dose or during any use of Merck's product that:

- Results in death;
- Is life threatening;
- Results in persistent or significant disability/incapacity;
- Results in or prolongs an existing inpatient hospitalization;
- Is a congenital anomaly/birth defect;
- causes another important medical event

• **Note:** In addition to the above criteria, adverse events meeting either of the below criteria, although not serious per ICH definition, are reportable to the Merck in the same timeframe as SAEs to meet certain local requirements. Therefore, these events are considered serious by Merck for collection purposes.

- Is a new cancer (that is not a condition of the study);
- Is associated with an overdose.

Refer to Table 7 for additional details regarding each of the above criteria.

For the time period beginning when the consent form is signed until treatment allocation/randomization, any serious adverse event, or follow up to a serious adverse event, including death due to any cause that occurs to any participant must be reported within 24 hours to the Sponsor and within 2 working days to Merck Global Safety if it causes the participant to be excluded from the trial, or is the result of a protocol-specified intervention, including but not limited to washout or discontinuation of usual therapy, diet, placebo treatment or a procedure.

For the time period beginning at treatment allocation/randomization through 90 days following cessation of treatment, or 30 days following cessation of treatment if the participant initiates new anticancer therapy, whichever is earlier, any serious adverse event, or follow up to a serious adverse event, including death due to any cause whether or not related to the Merck product, must be reported within 24 hours to the Sponsor and within 2 working days to Merck Global Safety.

Additionally, any serious adverse event, considered by an investigator who is a qualified physician to be related to Merck product that is brought to the attention of the investigator at any time following consent through the end of the specified safety follow-up period specified

in the paragraph above, or at any time outside of the time period specified in the previous paragraph also must be reported immediately to Merck Global Safety.

All participants with serious adverse events must be followed up for outcome.

SAE reports and any other relevant safety information are to be forwarded to the Merck Global Safety [contact]

A copy of all 15 Day Reports and Annual Progress Reports is submitted as required by FDA, European Union (EU), Pharmaceutical and Medical Devices agency (PMDA) or other local regulators. Investigators will cross reference this submission according to local regulations to the Merck Investigational Compound Number (IND, CSA, etc.) at the time of submission. Additionally, investigators will submit a copy of these reports to Merck & Co., Inc. (Attn: Worldwide Product Safety; [contact]) at the time of submission to FDA.

7.3.3.2 Events of Clinical Interest

Selected non-serious and serious adverse events are also known as Events of Clinical Interest (ECI) and must be reported within 2 working days to Merck Global Safety. (Attn: Worldwide Product Safety; [contact]).

For the time period beginning when the consent form is signed until treatment allocation/randomization, any ECI, or follow up to an ECI, that occurs to any participant must be reported within 2 working days to Merck Global Safety if it causes the participant to be excluded from the trial, or is the result of a protocol-specified intervention, including but not limited to washout or discontinuation of usual therapy, diet, placebo treatment or a procedure.

For the time period beginning at treatment allocation/randomization through 90 days following cessation of treatment, or 30 days following cessation of treatment if the participant initiates new anticancer therapy, whichever is earlier, any ECI, or follow up to an ECI, whether or not related to Merck product, must be reported within 2 working days to Merck Global Safety.

Events of clinical interest for this trial include:

1. an overdose of Merck product, as defined in Section 7.4.1 - Definition of an Overdose for This Protocol and Reporting of Overdose to the Sponsor and to Merck, that is not associated with clinical symptoms or abnormal laboratory results.
2. an elevated AST or ALT lab value that is greater than or equal to 3X the upper limit of normal and an elevated total bilirubin lab value that is greater than or equal to 2X the upper limit of normal and, at the same time, an alkaline phosphatase lab value that is less than 2X the upper limit of normal, as determined by way of protocol-specified laboratory testing or unscheduled laboratory testing.*

***Note:** These criteria are based upon available regulatory guidance documents. The purpose of the criteria is to specify a threshold of abnormal hepatic tests that may require an additional evaluation for an underlying etiology.

7.3.4 Evaluating Adverse Events

An investigator who is a qualified physician will evaluate all adverse events according to the NCI Common Terminology for Adverse Events (CTCAE), version 5.0. Any adverse event which changes CTCAE grade over the course of a given episode will have each change of grade recorded on the adverse event case report forms/worksheets.

All adverse events regardless of CTCAE grade must also be evaluated for seriousness.

This Phase II study is based on prior experience of the combination of p53MVA and pembrolizumab, and overlapping toxicities are not expected. However, we will monitor closely for toxicity. If there are more than 2 serious adverse events related to treatment on protocol in the first 9 subjects, the study will hold for toxicity review.

Table 7 Evaluating Adverse Events

An investigator who is a qualified physician, will evaluate all adverse events as to:

CTCAE V5.0 Grading	Grade 1	Mild; asymptomatic or mild symptoms; clinical or diagnostic observations only; intervention not indicated.
	Grade 2	Moderate; minimal, local or noninvasive intervention indicated; limiting age-appropriate instrumental ADL.
	Grade 3	Severe or medically significant but not immediately life-threatening; hospitalization or prolongation of hospitalization indicated; disabling; limiting self-care ADL.
	Grade 4	Life threatening consequences; urgent intervention indicated.
	Grade 5	Death related to AE
Seriousness	
A serious adverse event is any adverse event occurring at any dose or during any use of Merck product that:
 
†Results in death; or
 
†Is life threatening; or places the participant, in the view of the investigator, at immediate risk of death from the event as it occurred (Note: This does not include an adverse event that, had it occurred in a more severe form, might have caused death.); or
 
†Results in a persistent or significant disability/incapacity (substantial disruption of one's ability to conduct normal life functions); or
 
†Results in or prolongs an existing inpatient hospitalization (hospitalization is defined as an inpatient admission, regardless of length of stay, even if the hospitalization is a precautionary measure for continued observation. (Note: Hospitalization for an elective procedure to treat a pre-existing condition that has not worsened is not a serious adverse event. A pre-existing condition is a clinical condition that is diagnosed prior to the use of a Merck product and is documented in the patient's medical history.); or
 
†Is a congenital anomaly/birth defect (in offspring of participant taking the product regardless of time to diagnosis); or
 
Is a new cancer (that is not a condition of the study) (although not serious per ICH definition, is reportable to the Sponsor within 24 hours and to Merck within 2 working days to meet certain local requirements); or
 
Is an overdose (whether accidental or intentional). Any adverse event associated with an overdose is considered a serious adverse event for collection purposes. An overdose that is not associated with an adverse event is considered a non-serious event of clinical interest and must be reported within 24 hours to the Sponsor and to Merck within 2 working days.
	

	Other important medical events that may not result in death, not be life threatening, or not require hospitalization may be considered a serious adverse event when, based upon appropriate medical judgment, the event may jeopardize the participant and may require medical or surgical intervention to prevent one of the outcomes listed previously (designated above by a †).						
Duration	Record the start and stop dates of the adverse event. If less than 1 day, indicate the appropriate length of time and units						
Action taken	Did the adverse event cause Merck product to be discontinued?						
Relationship to Merck Product	
Did Merck product cause the adverse event? The determination of the likelihood that Merck product caused the adverse event will be provided by an investigator who is a qualified physician. The investigator's signed/dated initials on the source document or worksheet that supports the causality noted on the AE form, ensures that a medically qualified assessment of causality was done. This initialed document must be retained for the required regulatory time frame. The criteria below are intended as reference guidelines to assist the investigator in assessing the likelihood of a relationship between the test drug and the adverse event based upon the available information.
 
The following components are to be used to assess the relationship between Merck product and the AE; the greater the correlation with the components and their respective elements (in number and/or intensity), the more likely Merck product caused the adverse event (AE):
 
 
 Exposure	Is there evidence that the participant was actually exposed to Merck product such as: reliable history, acceptable compliance assessment (pill count, diary, etc.), expected pharmacologic effect, or measurement of drug/metabolite in bodily specimen?	
 
 Time Course	Did the AE follow in a reasonable temporal sequence from administration of Merck product? Is the time of onset of the AE compatible with a drug-induced effect (applies to trials with investigational medicinal product)?	
 
 Likely Cause	Is the AE not reasonably explained by another etiology such as underlying disease, other drug(s)/vaccine(s), or other host or environmental factors	
 
	Exposure	Is there evidence that the participant was actually exposed to Merck product such as: reliable history, acceptable compliance assessment (pill count, diary, etc.), expected pharmacologic effect, or measurement of drug/metabolite in bodily specimen?	Time Course	Did the AE follow in a reasonable temporal sequence from administration of Merck product? Is the time of onset of the AE compatible with a drug-induced effect (applies to trials with investigational medicinal product)?	Likely Cause	Is the AE not reasonably explained by another etiology such as underlying disease, other drug(s)/vaccine(s), or other host or environmental factors
Exposure	Is there evidence that the participant was actually exposed to Merck product such as: reliable history, acceptable compliance assessment (pill count, diary, etc.), expected pharmacologic effect, or measurement of drug/metabolite in bodily specimen?						
Time Course	Did the AE follow in a reasonable temporal sequence from administration of Merck product? Is the time of onset of the AE compatible with a drug-induced effect (applies to trials with investigational medicinal product)?						
Likely Cause	Is the AE not reasonably explained by another etiology such as underlying disease, other drug(s)/vaccine(s), or other host or environmental factors						

Relationship to Merck Product (continued)	The following components are to be used to assess the relationship between the test drug and the AE: (continued)	
	Dechallenge	
Was Merck product discontinued or dose/exposure/frequency reduced?
 
If yes, did the AE resolve or improve?
 
If yes, this is a positive dechallenge. If no, this is a negative dechallenge.
 
(Note: This criterion is not applicable if: (1) the AE resulted in death or permanent disability; (2) the AE resolved/improved despite continuation of the Sponsor's product; or (3) the trial is a single-dose drug trial); or (4) Sponsor's product(s) is/are only used one time.)

	Rechallenge	
Was the participant re-exposed to Merck product in this study?
 
If yes, did the AE recur or worsen?
 
If yes, this is a positive rechallenge. If no, this is a negative rechallenge.
 
(Note: This criterion is not applicable if: (1) the initial AE resulted in death or permanent disability, or (2) the trial is a single-dose drug trial); or (3) Sponsor's product(s) is/are used only one time).
 
NOTE: IF A RECHALLENGE IS PLANNED FOR AN ADVERSE EVENT WHICH WAS SERIOUS AND WHICH MAY HAVE BEEN CAUSED BY MERCK PRODUCT, OR IF REEXPOSURE TO MERCK PRODUCTPOSES ADDITIONAL POTENTIAL SIGNIFICANT RISK TO THE PARTICIPANT, THEN THE RECHALLENGE MUST BE APPROVED IN ADVANCE BY THE SPONSOR AS PER DOSE MODIFICATION GUIDELINES IN THE PROTOCOL.

Consistency with Trial Treatment Profile	Is the clinical/pathological presentation of the AE consistent with previous knowledge regarding Merck product or drug class pharmacology or toxicology?	
The assessment of relationship will be reported on the case report forms /worksheets by an investigator who is a qualified physician according to his/her best clinical judgment, including consideration of the above elements.		
Record one of the following	Use the following scale of criteria as guidance (not all criteria must be present to be indicative of Merck product relationship).	
Yes, there is a reasonable possibility of Merck product relationship.	There is evidence of exposure to Merck product. The temporal sequence of the AE onset relative to the administration of Merck product is reasonable. The AE is more likely explained by Merck product than by another cause.	
No, there is not a reasonable possibility of Merck product relationship	Participant did not receive the Merck product OR temporal sequence of the AE onset relative to administration of Merck product is not reasonable OR the AE is more likely explained by another cause than the Merck product. (Also entered for a participant with overdose without an associated AE.)	

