2.0 TRIAL DESIGN

2.1 Trial Design

This is a Phase II, single center study enrolling 16-28 patients. Patients will be initially enrolled at a single dose level and dose de-escalation of p53MVA will be employed if necessary.

Single arm: *p53MVA* (dose 5.0 x10⁸ pfu) + *pembrolizumab* (anti-PD1 mAb flat dose: 200 mg)

p53MVA and pembrolizumab will be given concurrently in accordance with previous studies that show potential for checkpoint inhibitors in combination with vaccines. The aim is to use pembrolizumab to enhance the activity of the p53MVA vaccine to deliver clinical benefit:

Treatment Schedule:

Week 1 (day 1): p53MVA + pembrolizumab

Week 4: p53MVA + pembrolizumab

Week 7: p53MVA + pembrolizumab

[figure not shown]
Week 10: pembrolizumab

Week 13: pembrolizumab

Week 16: pembrolizumab continuing every 3 weeks up to 35 cycles (105 weeks)*

(Pembrolizumab treatment may be extended beyond 49 weeks if a second course is indicated, see Section 5.2.3)

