5.2.1 Timing of Dose Administration

Trial treatment should be administered on Day 1 of each cycle after all procedures/assessments have been completed as detailed on the Trial Flow Chart (Section 6.0). Trial treatment may be administered up to 5 days before or after the scheduled Day 1 of each cycle due to administrative reasons. All trial treatments will be administered on an outpatient basis. Pembrolizumab 200 mg will be administered as a 30 minute IV infusion every 3 weeks. Sites should make every effort to target infusion timing to be as close to 30 minutes as possible. However, given the variability of

infusion pumps from site to site, a window of -5 minutes and +10 minutes is permitted (i.e., infusion time is 30 minutes: -5 min/+10 min). The Merck Pharmacy Manual contains specific instructions for the preparation of the pembrolizumab infusion fluid and administration of infusion solution. Section 9.0 of this protocol contains instructions for preparation and handling of the p53MVA vaccine.

5.2.2 Dose Modification and toxicity management for immune-related AEs associated with pembrolizumab

AEs associated with pembrolizumab exposure may represent an immunologic etiology. These immune-related AEs (irAEs) may occur shortly after the first dose or several months after the last dose of pembrolizumab treatment and may affect more than one body system simultaneously. Therefore, early recognition and initiation of treatment is critical to reduce complications. Based on existing clinical study data, most irAEs were reversible and could be managed with interruptions of pembrolizumab, administration of corticosteroids and/or other supportive care. For suspected irAEs, ensure adequate evaluation to confirm etiology or exclude other causes. In order to monitor for immune mediated hyperthyroidism and hypothyroidism, patients will be assessed for thyroid function (TSH) at baseline. TSH testing will be repeated during/after the treatment phase if clinical signs and symptoms of thyroid disorders are observed. Additional procedures or tests such as bronchoscopy, endoscopy, skin biopsy may be included as part of the evaluation. Based on the severity of irAEs, withhold or permanently discontinue pembrolizumab and administer corticosteroids. Dose modification and toxicity management guidelines for irAEs associated with pembrolizumab are provided in Table 3.

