7.2 City of Hope Data and Safety Monitoring

7.2.1 Risk Determination

This is a high risk study, as defined in the [City of Hope Institutional DSMP](#). This determination was made because the study involves a COH held IND for p53MVA and off label use of a commercially available product, Pembrolizumab. This is a combined immunotherapy study of vaccine and antibody. As p53MVA does not integrate into host DNA, this study is NOT classified as gene therapy. p53MVA has already been tested in 20 human subjects at COH (IRB#10105 and IRB#13373). Pembrolizumab is FDA approved for two indications. A study testing the combination of p53MVA and Pembrolizumab is underway at COH (IRB#15002). This will be the second study testing the two agents in combination.

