7.2.5 Protocol Management Team (PMT)

The Protocol Management Team (PMT), minimally consisting of the study PI, collaborating investigator, research nurse, clinical research associate/coordinator, and the study biostatistician, is responsible for ongoing monitoring the data and safety of this study, including implementation of the stopping rules for safety/toxicity.

The PMT is recommended to meet (in person or via teleconference) to review study status. The meeting is a forum to discuss study related issues including accrual, SAE/AE/UPs experienced, study response, deviations/violations, and study management issues. The appropriateness of further subject enrollment and the specific intervention for subsequent subject enrollment are addressed.

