8.2 Statistical Analysis Plan

Sample Size Accrual Rate

Study size is based on our therapeutic target of achieving with acceptable toxicity a considerable improvement in the response rate observed with single agent pembrolizumab in this patient population, previously reported as 8% (KEYNOTE-100). Specifically, we seek to have good power to detect an improvement in the response rate to 25%. To achieve this, Simon's MiniMax two-stage design is employed to have 85% power to detect a true promising response rate of 25%, with a type I error of 8% for declaring a true discouraging response rate of 8% as worthy of further consideration: Initially, 17 patients will be enrolled for the first stage. If 2 or more patients experience a response during the first stage, accrual will continue to 28 patients. With a total of 28 patients, at least 5 responders (18%) is the minimum to determine the combination worthy of further consideration. This design has a 60% chance of early stopping if the true response rate is 8%. Final determination of promise will be based on the totality of the clinical endpoints and consideration of the profile of patients' PDL-1 expression, where a different accrual pattern when compared to KEYNOTE-100 may require a higher or lower threshold for the final decision. Expected accrual rate is approximately one patient every one and ½ months.

Analysis of Biological Correlates

Peripheral blood samples will be collected pre- and post-immunization for assessment of anti-p53 T cell responses and immunophenotyping. Immunosuppressive cell types (MDSC, Tregs) and other selected lymphocyte subsets and markers including PD-1, PDL-1 and PDL-2 will be quantified. Secondary endpoints will be clinical responses and T cell reactivity to p53. These

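### The only numeric toxicity hold ends at subject 9, so 8 of 17 patients (or 19 of 28 at full accrual) have qualitative safety review only

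*Combined protocol and SAP*

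**What the plan says.** Section 7.3.4 sets the rule: "If there are more than 2 serious adverse events related to treatment on protocol in the first 9 subjects". When that happens, "the study will hold for toxicity review". The unit is the serious adverse event, the trigger is three or more, and the consequence is a pause for review, not termination. No time window is attached to the nine subjects.

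Section 7.2.5 makes the Protocol Management Team responsible for safety monitoring, "including implementation of the stopping rules for safety/toxicity", but states no rule there. The other safety provisions carry no trial-level number:

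- Section 5.6, item 3, allows early termination if the incidence or severity of adverse reactions points to a health hazard, without a threshold.
- Section 7.2.2 has the Data and Safety Monitoring Committee review toxicity, without a threshold.
- Tables 3, 4A and 4B govern the management of individual patients.
- Section 8 contains no safety boundary, although the study-size paragraph of Section 8.2 and the hypothesis in Section 3.1 both include acceptable toxicity.

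On accrual, Section 8.2 says: "Initially, 17 patients will be enrolled for the first stage", and then "If 2 or more patients experience a response during the first stage, accrual will continue to 28 patients".

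**The concern.** A numeric hold gives the monitoring team a result it must act on. Here that protection stops at subject 9, and the plan gives no second numeric check. If the first nine patients happen to look acceptable while the true related-SAE rate is high, everyone enrolled afterwards depends on judgement alone. The reference in Section 7.2.5 to stopping rules suggests that more was intended than one early check. A conclusion of acceptable toxicity would also be easier to defend if it had been tested against a stated boundary through the whole of accrual.

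A second issue is the unit. Three related SAEs in one patient meet the trigger just as three affected patients do. The documents do not say whether this is deliberate, and the rule behaves differently under the two readings.

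**Working it through.** **Inputs.** From the documents: trigger of 3 or more in the first 9 (Section 7.3.4); stage 1 of 17 and maximum of 28 (Section 8.2). The documents give no treatment-related SAE rate and no number of SAEs per affected patient, so both are assumed over a range.

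**The plan's own figures.** The hold rule has no stated operating characteristics to reproduce. The efficacy design that fixes the accrual steps does reproduce. Early stopping at an 8% response rate is P(X ≤ 1 of 17) = 0.92^17 + 17 × 0.08 × 0.92^16 = 0.242 + 0.358 = 0.6005 (stated 60%). Power at 25% is 0.8515 (stated 85%).

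**Patients beyond the rule.** 17 − 9 = 8 (47%) if the trial stops at stage 1; 28 − 9 = 19 (68%) at full accrual.

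**First nine only, counting patients.** With independent patients, each having at least one related SAE with probability p, P(hold) = 1 − P(X ≤ 2 of 9).

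- p = 10%: 1 − (0.3874 + 0.3874 + 0.1722) = 0.053
- p = 30%: 1 − (0.0404 + 0.1557 + 0.2668) = 0.537
- p = 40%: 1 − (0.0101 + 0.0605 + 0.1612) = 0.768

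**Adding a look at 17.** The present trigger is 3 in 9, one-third if each affected patient has one event. Carried forward, it becomes 6 or more of 17 and 9 or more of 28 affected patients. The added probability at 17 is the sum over x = 0, 1, 2 of P(X = x of 9) × P(Y ≥ 6 − x of 8).

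- p = 30%: 0.0404 × 0.0113 + 0.1557 × 0.0580 + 0.2668 × 0.1941 = 0.061, total 0.598
- p = 40%: 0.0101 × 0.0498 + 0.0605 × 0.1737 + 0.1612 × 0.4059 = 0.076, total 0.845

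The step to 28 is calculated in the same way and assumes that the trial goes on to stage 2.

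| True rate | First 9 only | Looks at 9 and 17 | Looks at 9, 17 and 28 |
|---|---|---|---|
| 10% | 5.3% | 5.4% | 5.4% |
| 20% | 26.2% | 28.2% | 30.2% |
| 30% | 53.7% | 59.8% | 67.4% |
| 40% | 76.8% | 84.5% | 92.0% |

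**The rule as written, counting events.** Let each affected patient have 1 + Poisson(μ) related SAEs, and hold if the first nine have three or more in total (simulated).

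| Affected | Mean 1 SAE each | Mean 1.5 | Mean 2 |
|---|---|---|---|
| 10% | 5% | 20% | 30% |
| 20% | 26% | 48% | 60% |
| 30% | 54% | 72% | 81% |

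Keeping this event-counted rule on the first nine and adding the patient-counted look at 17, in the same simulation, moves the 30% row from 72% to 75% at mean 1.5 and from 81% to 82% at mean 2. At 10% affected and mean 1.5 it stays at 20%.

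**The case against.** **The miss rates describe a rule that the protocol does not contain.** This stands. The 46% chance of no hold at a 30% rate (1 − 0.537) counts patients, whereas the text counts events. Event counting can only make the first-nine rule more sensitive. With an assumed mean of 1.5 SAEs per affected patient, the present rule triggers about 72% of the time at 30% affected, more than the 67.4% from three patient-counted looks. Replacing events by patients therefore loses early sensitivity; what it buys is fewer false holds (about 20% down to 5% at 10% affected).

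**A look at 28 protects no accrual.** This stands. It can bear only on patients still receiving study treatment, so the gain before accrual ends is the one from the look at 17.

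**Later patients are not unmonitored.** This also stands. A reader might infer that they have no safety protection. The team and committee reviews and Section 5.6 cover everyone; what is missing is a number.

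**Late toxicity.** Section 5.2.2 says that immune-related events "may occur shortly after the first dose or several months after the last dose of pembrolizumab treatment", and a reader might infer that the rule is blind to them. It is not: Section 7.3.4 limits the subjects, not the time, so a late related SAE in any of the first nine still counts.

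**The risk label.** Section 7.2.1 says "This is a high risk study, as defined in the" institutional monitoring plan, but bases this on the IND held by the institution and off-label use. It is not a forecast of high toxicity. Section 7.3.4 also cites prior experience with the combination and expects no overlapping toxicity, which is a fair reason for a light early check, though not for having no numeric check afterwards.

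**Conclusion.** The point holds as a gap in numeric monitoring after subject 9, plus an unstated choice of counting unit. It affects 8 patients if the trial stops at stage 1 and 19 only at full accrual. A reader might take 19 of 28 as the general figure, but Section 8.2 itself gives a 60% chance of stopping at 17 if the response rate is 8%.

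The gain from one added look is moderate. Counting patients throughout, it is 6.1 percentage points at a 30% rate (59.8 − 53.7) and 7.7 at 40% (84.5 − 76.8), for 0.1 point at 10%. It is smaller if the first-nine rule keeps counting events and patients have several each. Put differently, if no hold occurs in the first nine, the chance of a numeric hold by subject 17 goes from zero to 13% at a 30% rate (0.061/0.463) and 33% at 40% (0.076/0.232).

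These figures rest on independent patients, a constant rate and the assumed ranges. The size of the benefit depends on those assumptions; the absence of a numeric rule after subject 9 does not.

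**What to change.** In Section 7.3.4, with a cross-reference from Sections 7.2.5 and 8.2:

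1. Keep the early hold on the first nine, and state whether it counts events or patients with at least one related SAE. If it changes to patients, acknowledge the loss of early sensitivity shown above.
2. Add a later hold for review that carries the same proportion forward in affected patients, for example more than 5 of 17 at the stage-1 look. A further check of more than 8 of 28 could be added, described as informing review of patients still on treatment. The thresholds illustrate the plan's own one-third trigger; the related-SAE rate that is tolerable is for the sponsor to set.
3. Report the operating characteristics of the whole rule over an assumed range of related-SAE rates.
4. Settle the stage-1 number. Section 2.1 says "This is a Phase II, single center study enrolling 16-28 patients", while Section 8.2 uses 17, and only 17 reproduces the stated 60% (16 gives 63%).

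The cost is a few sentences and a small table. Sample size and efficacy design do not change, and the look at 17 coincides with a decision that already needs data on those patients. The price is slightly more temporary holds: 0.1 point at a 10% rate and 2.0 points at 20% (28.2 − 26.2).
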